7.2.2.5.3 Urinalysis

Urinalysis samples will be collected at screening visit 1, week 1/day 1, and at monthly visits from week 4 through end of treatment as detailed in [Table 7-1](#). A midstream second voided

morning sample will be obtained. Dipstick measurements for specific gravity, pH, blood, white blood cells, glucose, protein, bilirubin, color, nitrite, urobilinogen and ketones will be assessed at the local site. Microscopic analysis will be performed only in case of a positive dipstick result for protein. Dipsticks will be supplied by a local laboratory. Any significant findings on dipstick will be followed up with a microscopic evaluation where WBC and RBC sediments will also be measured. If ketones are positive, measurement of hemoglobin A1C and/or fasting pre-prandial glucose may be performed by the local laboratory at the request of the Investigator.

At screening visit 1 and in addition to the dipstick measurement, a urine sample (at least 15 mL) will be collected and sent to a local laboratory for urinary protein/creatinine ratio to assess the eligibility of the patient. In addition, urine samples for urinary protein/creatinine ratios will be collected at week 1/day 1 and at monthly visits, weeks 4 through end of treatment. First morning void samples must not be used for this analysis. Significant protein is indicated by a urinary protein/creatinine ratio >0.5 mg/mg.

For patients who develop proteinuria or worsening of pre-existing proteinuria (assessed by dipstick) at any visit, microscopic analysis must be performed by the local laboratory.

All urinalysis samples will be sent to a local laboratory.

7.2.2.6 Ocular assessments

Ocular assessments will be performed at screening visit 1 and at end of treatment according to the local (institution's) clinical practice. The choice of method for ocular assessments will be at the discretion of the investigators. Best efforts should be made to perform these assessments in all subjects, although feasibility in very young children will be at the discretion of the investigator. Additional ocular assessment is permitted at the discretion of the Investigator based on patient reporting of symptoms.

7.2.2.7 Auditory assessments

Auditory assessments will be performed at screening visit 1 and at end of treatment according to local (institution's) clinical practice. The choice of method for auditory assessments will be at the discretion of the investigators. Best efforts should be made to perform these assessments in all subjects, although feasibility in very young children will be at the discretion of the investigator. Additional auditory assessment is permitted at the discretion of the Investigator based on patient reporting of symptoms.

7.2.2.8 Pregnancy and assessments of fertility

Not applicable

7.2.2.9 Radiological examinations

Not applicable

7.2.2.10 Cardiac assessments

Not applicable

7.2.2.10.1 Electrocardiogram (ECG)

A standard 12 lead ECG will be performed at screening visit 1.

Interpretation of the tracing must be made by a qualified physician and documented on the ECG CRF page. Each ECG tracing should be labeled with the study number, patient initials (where regulations permit), patient number, date, and kept in the source documents at the study site. Clinically significant abnormalities present at screening should be reported on the Medical History CRF page. Clinically significant findings must be discussed with Novartis prior to enrolling the patient in the study. New or worsened clinically significant findings occurring after informed consent must be recorded on the Adverse Events CRF page.

Additional, unscheduled, safety ECGs may be repeated at the discretion of the investigator at any time during the study as clinically indicated. Local cardiologist ECG assessment may also be performed at any time during the study at the discretion of the investigator.

7.2.2.10.2 Cardiac imaging - MRA (magnetic resonance angiography), MUGA (multiple gated acquisition) scan or echocardiogram

Not applicable

7.2.2.10.3 Cardiac enzymes

Not applicable

7.2.2.11 Tolerability

Patients and/or their caregivers will complete an electronic palatability questionnaire as detailed in Table 7-1 and provided in the Appendix 14.1.

7.2.3 Limitations of the study

Novartis will carefully ensure that the PASS will not interfere/modify the local medical practices. The sites will be selected based on their transfusional hemosiderosis treatment experience and patients will be enrolled even if they already started chelation for this indication. Novartis will interact with local networks to ensure targeting the best representation as possible. Therefore, no limitation of potential selection bias is expected in this trial.

The limitations of the research may be a small sample size.

7.2.4 Pharmacokinetics

Not applicable

7.2.4.1 Analytical method

Not applicable

7.2.5 Biomarkers

Not applicable

7.2.5.1 Additional biomarker assessments

Not applicable

7.2.5.1.1 Optional additional exploratory biomarker assessments using remaining biomarker samples

Not applicable

7.2.6 Other assessments

No additional tests will be performed on patients entered into this study.

7.2.7 Resource utilization

Not applicable

7.2.8 Patient reported outcomes

As detailed in [Table 7-1](#) and provided in Appendix 14.1, patients or their caregivers will complete a series of ObsRO questionnaires at the study site (during study visits) as follows:

- palatability and mSCIT of crushed FCT, at SV1 and at the following visits: week 4, week 12 and at end of treatment
- gastrointestinal symptoms of crushed FCT at SV1 and at the following visits: week 2, week 3, week 4, week 8, week 12, week 16, week 20 and at end of treatment

Note: Chelation naïve patients and patients treated with chelation therapy who stopped treatment more than 7 days prior to Screening visit 1 will not complete questionnaires at screening.

8 Safety monitoring and reporting

8.1 Adverse events

8.1.1 Definitions and reporting

An adverse event is defined as the appearance of (or worsening of any pre-existing) undesirable sign(s), symptom(s), or medical condition(s) that occur after patient's signed informed consent has been obtained.

Abnormal laboratory values or test results occurring after informed consent constitute adverse events only if they induce clinical signs or symptoms, are considered clinically significant, require therapy (e.g., hematologic abnormality that requires transfusion or hematological stem cell support), or require changes in study medication(s).

Adverse events that begin or worsen after informed consent should be recorded in the Adverse Events CRF. Conditions that were already present at the time of informed consent should be recorded in the Medical History page of the patient's CRF. Adverse event monitoring should be continued for at least 30 days following the last dose of study treatment. Adverse events (including lab abnormalities that constitute AEs) should be described using a diagnosis

whenever possible, rather than individual underlying signs and symptoms. When a clear diagnosis cannot be identified, each sign or symptom should be reported as a separate Adverse Event.

Adverse events will be assessed according to severity: mild, moderate or severe. Information about any deaths (related to an Adverse Event or not) will also be collected through a Death form.

The occurrence of adverse events should be sought by non-directive questioning of the patient (subject) during the screening process after signing informed consent and at each visit during the study. Adverse events also may be detected when they are volunteered by the patient (subject) during the screening process or between visits, or through physical examination, laboratory test, or other assessments. As far as possible, each adverse event should be evaluated to determine:

1. Severity (Mild, moderate or severe)
2. Its duration (Start and end dates)
3. Its relationship to the study treatment (Reasonable possibility that AE is related: No, Yes)
4. Action taken with respect to study or investigational treatment (none, dose adjusted, temporarily interrupted, permanently discontinued, unknown, not applicable)
5. Whether medication or therapy was given (no concomitant medication/non-drug therapy, concomitant medication/non-drug therapy)
6. Whether it is serious, where a serious adverse event (SAE) is defined as in Section 8.2.1 and which seriousness criteria have been met
7. Outcome (not recovered/not resolved, recovered/resolved, recovering/resolving, recovered/resolved with sequelae, fatal, unknown).

If the event worsens the event should be reported a second time in the CRF noting the start date when the event worsens in toxicity. For moderate and severe events, if improvement to a lower grade is determined a new entry for this event should be reported in the CRF noting the start date when the event improved.

All adverse events should be treated appropriately. If a concomitant medication or non-drug therapy is given, this action should be recorded on the Adverse Event CRF.

Once an adverse event is detected, it should be followed until its resolution or until it is judged to be permanent, and assessment should be made at each visit (or more frequently, if necessary) of any changes in severity, the suspected relationship to the study treatment, the interventions required to treat it, and the outcome. Follow up will continue up to 30 days after study drug discontinuation.

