8.1.3 Adverse events of special interest

Adverse events of special interest (AESI) are defined as events (serious or non-serious) which are ones of scientific and medical concern specific to the sponsor's product or program, for which ongoing monitoring and rapid communication by the investigator to the sponsor may be appropriate. Such events may require further investigation in order to characterize and understand them.

Adverse events of special interest are defined on the basis of an ongoing review of the safety data. AESIs are discussed in detail in the Investigator Brochure.

Selected AEs, especially related to disturbances of the gastrointestinal tract, will be collected and assessed for severity: esophagitis, stomatitis, mouth ulceration, gastric ulcers, hemorrhage, abdominal pain, diarrhea, nausea, and vomiting.

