10.4.2 Statistical hypothesis, model, and method of analysis

Proportion of patients with selected GI disorders will be provided together with the 95% confidence interval using the Clopper-Pearson exact method for this proportion.

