10.8 Sample size calculation

This study is designed to enroll a minimum of 40 patients. Statistical computations were performed (see table below) to evaluate probabilities to observe at least one patient with an AE given 40 patients and different scenarios of AE incidence rates (Hanely and Lippman- Hand 1983). This table shows a reasonable chance to observe AE events occurring with an incidence of 3% or higher together with the 95% Clopper-Pearson confidence interval (CI) for the incidence rate.

Table 10-1 Clopper-Pearson 95% CI for different incidence of AEs and the corresponding probability to observe at least one AE

Incidence of AE	Clopper-Pearson 95% CI for the incidence rate	Probability that at least one patient out of 40 experiences that AE
3%	(0.00, 0.14)	0.70
4%	(0.00, 0.15)	0.80
5%	(0.01, 0.17)	0.87
6%	(0.01, 0.18)	0.92
7%	(0.01, 0.20)	0.95
10%	(0.03, 0.24)	0.99
15%	(0.06, 0.30)	1.00
20%	(0.09, 0.36)	1.00
25%	(0.13, 0.41)	1.00
30%	(0.17, 0.47)	1.00

11 Ethical considerations and administrative procedures

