2.8.1 Primary endpoint

The primary endpoint is the proportion of patients with selected gastrointestinal disorders (esophagitis, stomatitis, mouth ulceration, gastric ulcers, hemorrhage, abdominal pain, diarrhea,

nausea, and vomiting) up to 24 weeks including 30 days safety follow-up. Selected gastrointestinal disorders will be captured from AE page of eCRFs and PT term will be used. Corresponding PT terms will be oesophagitis, Barrett's esophagitis, stomatitis, mouth ulceration, gastric ulcer, gastrointestinal haemorrhage, abdominal pain, diarrhoea, nausea and vomiting. If patients discontinue earlier than 24-week visit, the patients will be followed 30 days after discontinuation of study treatment.

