2.11.1.1 Adverse events of special interest / grouping of AEs

Specific groupings of adverse events of special interest will be considered and the number of patients with at least one event in each grouping will be reported. Such groups consist of adverse events for which there is a specific clinical interest in connection with deferasirox treatment. Note that certain adverse events will be reported within multiple groupings/AESIs. AESIs are defined by MedDRA terms. Definition for retrieval (maintenance of terms considered AESI) is in case retrieval strategy (eCRS). To select the corresponding records from SAS dataset ECRS in Novartis computing environment, use

- Compound name = “ICL670”,
- Compound indication = “ICL670 Chronic iron overload”
- and records without CRS Version End Date, means the latest version.

All safety topics flagged in the eCRS using the core safety flag will be considered for the analysis.

AESI will be summarized regardless of study drug relationship, by grouping, preferred term. Gastrointestinal AEs will also be summarized as a part of AESI.

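### Recording a diagnosis in place of its symptoms can drop a child from the primary GI rate, which counts only ten named preferred terms

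*Protocol*

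**What the plan says.** **Recording rule.** Protocol 8.1.1 tells sites that adverse events should be described by a diagnosis where one can be made: "whenever possible, rather than individual underlying signs and symptoms. When a clear diagnosis cannot be identified, each sign or symptom should be reported as" (that is, as an event of its own). Symptoms are therefore the fallback for when no clear diagnosis exists.

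**Counting rule.** SAP 2.8.1 fixes the source of the primary endpoint: "Selected gastrointestinal disorders will be captured from AE page of eCRFs and PT term will be used". It then gives the list: "Corresponding PT terms will be oesophagitis, Barrett's esophagitis, stomatitis, mouth ulceration, gastric ulcer, gastrointestinal haemorrhage, abdominal pain, diarrhoea, nausea and vomiting". No other adverse event term and no other data source enters the primary proportion.

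**Related text.** Protocol 8.1.3 says of the selected events: "Selected AEs, especially related to disturbances of the gastrointestinal tract, will be collected and assessed for severity". It sets out no exception to 8.1.1 and no separate form. Protocol 10.5.3.2 lists the same events as adverse events of special interest to be tabulated. SAP 2.11.1.1 adds a separate output: "Gastrointestinal AEs will also be summarized as a part of AESI". Handling of missing values for the primary endpoint is marked not applicable in both documents, as are sensitivity analyses in Protocol 10.4.4. The one supportive analysis, the exposure-adjusted incidence in SAP 2.8.4, uses the same selected disorders.

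**The concern.** The two rules pull against each other for the four symptom terms. The primary endpoint counts occurrences whatever their cause, so a vomiting child belongs in the numerator whether the vomiting comes from the drug or from an infection. Under 8.1.1, however, the presence of a clear diagnosis is the reason to leave the symptom off the page. Two sites could see the same illness, enter it differently, and produce one primary event and none.

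At stake is the study's main result. Protocol 2.1 explains that the European authority asked for data on exactly these named events in young children taking crushed tablets. If the recorded proportion depends partly on labelling habit, it is harder to interpret and harder to compare across sites. The mechanism is plausible in this population: Protocol 1.2 reports that GI disorders and infections were the most commonly affected organ classes in the earlier paediatric studies, so GI symptoms with an infectious diagnosis should be expected.

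**Working it through.** **Step 1: follow one child through both rules.** Suppose a child has vomiting and diarrhoea and the site makes a clear diagnosis of gastroenteritis.

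- Under Protocol 8.1.1, one record is entered: gastroenteritis.
- Under SAP 2.8.1, that term is compared with the ten listed terms. It matches none.
- The child contributes no primary event unless another listed term is recorded at some point from first dose to 30 days after last dose.

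If the site enters vomiting and diarrhoea instead, the child counts. Listed lesions such as oesophagitis or gastric ulcer do not have this problem, because there the diagnosis is itself a counted term.

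**Step 2: look for a passage that repairs it.** Protocol 8.1.3 and 10.5.3.2 name the events but do not override the diagnosis rule. The special-interest grouping works from the same adverse event records, so it cannot recover a symptom that was never entered, and it does not feed the primary proportion. The exposure-adjusted incidence has the same gap. The GI symptom questionnaire (SAP 2.13.3) is analysed separately.

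**Step 3: direction and size.** Protocol 10.8 states: "This study is designed to enroll a minimum of 40 patients". Each child not counted lowers the proportion by 1/n. At n = 40 this is 1/40 = 2.5 percentage points.

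The plan specifies a 95% "confidence interval using the Clopper-Pearson exact method for this proportion". With B the beta quantile, the limits are B(0.025; x, n − x + 1) and B(0.975; x + 1, n − x). The plan's own Table 10-1 reproduces with this method. For 3%, the chance of at least one event is 1 − 0.97^40 = 0.704 (table: 0.70). With x = 40 × 0.03 = 1.2, the interval is 0.0013 to 0.1394 (table: 0.00, 0.14). All ten rows agree to two decimals; nothing in that table is disputed.

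The documents do not say how many children would be lost, so the table below only shows scale. The starting counts are assumptions: 16/40 takes the 40% for GI disorders in Protocol 1.2, and 10/40 takes the 26% in Protocol 1.2.1.2 (40 × 0.26 = 10.4, rounded to 10).

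| Children not counted (assumed) | From 16/40: rate (95% CI) | From 10/40: rate (95% CI) |
|---|---|---|
| 0 | 40.0% (24.9–56.7) | 25.0% (12.7–41.2) |
| 1 | 37.5% (22.7–54.2) | 22.5% (10.8–38.5) |
| 2 | 35.0% (20.6–51.7) | 20.0% (9.1–35.6) |
| 4 | 30.0% (16.6–46.5) | 15.0% (5.7–29.8) |

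Neither base rate is the rate of this endpoint. The 40% covers all GI disorders in observational dispersible-tablet studies lasting three to five years; the 26% covers GI disturbances in adults and children during chronic treatment.

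**The case against.** Preferring a diagnosis to its symptoms is ordinary adverse event practice, and the wording is *should, whenever possible*. When GI symptoms follow the crushed tablet and no other illness explains them, there is usually no clear diagnosis, so 8.1.1 itself has them entered as symptoms and they count. Mainly, then, the events at risk are those with another explanation. Protocol 8.1.3 names the four symptoms, and a site could reasonably take that specific statement as governing. The CRF completion guideline is not among the documents and may already settle the matter. The absorbing diagnosis still appears in the general adverse event tables. No hypothesis is tested, and every shifted estimate in the table lies inside the interval it started from.

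Most of this limits the size of the problem. It does not remove it. The endpoint has no causality restriction, so losing mainly unrelated illness still departs from its definition. A reading that a site could reasonably adopt is not an instruction, and if some sites adopt it and others do not, recording becomes inconsistent.

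A reader might infer that sites are obliged to suppress symptoms, or that drug-caused GI toxicity is systematically hidden. The documents support neither: the rule is not absolute, and symptoms without a clear diagnosis are entered individually.

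**Conclusion.** The conflict is real and neither document resolves it. Following both rules leaves a child out of the primary numerator when the child's only selected events are symptoms recorded under an unlisted diagnosis. The effect on the rate can only be downward, by 2.5 percentage points per such child at n = 40 and by less per child if more are enrolled.

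The total cannot be derived from the documents. It depends on how often a clear diagnosis is made, how sites label it, and how often the same child has another listed term during the on-treatment period. A reader might take the 40% background figure, apply a percentage loss, and conclude that the rate is understated by a known amount. That is not supported: the base is a different quantity, it is itself a reported rate that may already carry the same loss, and the documents give no loss percentage.

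The point deserves a change to the plan because the bias is one-directional, site-dependent, bears on the primary result, and is cheap to prevent.

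**What to change.** **Protocol 8.1.1 and 8.1.3.** State that each selected GI event is entered as its own adverse event record even when it is part of a diagnosis, and that the diagnosis is entered as well. Carry the same sentence into the CRF completion guideline.

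**SAP 2.8.4.** For records entered before that change, pre-specify a sensitivity count of the primary proportion. It adds children with any of a listed set of GI diagnosis preferred terms that would absorb the four symptoms, for example gastroenteritis and gastritis, with the list fixed before database lock. Report it beside the primary proportion with the same exact interval. It is not a strict bound: a listed diagnosis may have occurred without the symptoms, and a diagnosis outside the list would still be missed.

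The GI symptom questionnaire should stay a separate descriptive output and should not be used to correct the count. It asks only about the past week, has no causality field, has no baseline for chelation-naïve children, does not cover the 30-day follow-up, and the plan sets no cut-off that would turn an answer into an event.

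**Cost.** One sentence in the protocol and guideline, and one extra table. There will be more adverse event records, including infection-related symptoms, and a somewhat higher reported rate; the causality field allows related events to be shown separately. Seven patients had been enrolled by Amendment 1, so a later change leaves two recording conventions in one small study, and the report should say which records fall under which.

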10.4 Primary objective

The primary objective of the study is to assess the safety of crushed deferasirox FCT with respect to selected gastrointestinal (GI) disorders. Details regarding the analysis of AEs are described in [Section 10.5.3.2](#).

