10.5.3.2 Adverse events (AEs)

Summary tables for adverse events (AEs) will include only AEs that started or worsened during the on-treatment period, the ***treatment-emergent*** AEs.

The incidence of treatment-emergent adverse events (new or worsening from baseline) will be summarized by system organ class and or preferred term, severity, type of adverse event, relation to study treatment.

Serious adverse events and non-serious adverse events and adverse events of special interest (AESI: including esophagitis, stomatitis, mouth ulceration, gastric ulcers, hemorrhage, abdominal pain, diarrhea, nausea and vomiting) during the on-treatment period will be tabulated. The number and frequency of overall AEs and gastrointestinal AEs will be summarized for naïve (no ICT prior to enrollment) and non-naïve patients.

All deaths (on-treatment and post-treatment) will be summarized.

All AEs, deaths and serious adverse events (including those from the pre and post-treatment periods) will be listed and those collected during the pre-treatment and post-treatment period will be flagged.

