2.11.1 Adverse events (AEs)

All AEs recorded during the study are coded using the latest version of the medical dictionary for regulatory activities (MedDRA). Adverse events will not be assessed according to the common terminology criteria for AEs (CTCAE); instead, AE severity (mild, moderate, severe) will be used to report treatment-emergent AEs starting on or after the date of first study medication (including AEs that start within 30 days after the discontinuation of the study medication).

Frequency tables for treatment-emergent AEs will be presented. The summary tables will include the number of patients, and the percentage of patients experiencing the AE. Multiple occurrences of the same event in the same patient will be counted only once in the frequency tables. However, all adverse events will be included in the AE listings.

Frequency tables will display at least the MedDRA system organ class or preferred term, AE severity (mild, moderate, severe) or both, and relationship to study treatment. The following tables will be generated based on the data up-to 24 weeks including 30 days follow-up:

- Adverse events, regardless of study treatment relationship
- Adverse events, suspected to be study treatment related
- Serious adverse events, regardless of study treatment relationship
- Serious adverse events, suspected to be study treatment relationship
- Adverse events leading to study drug discontinuation, regardless of study treatment relationship
- Adverse events leading to study drug discontinuation, suspected to be study treatment relationship
- Adverse events requiring dose adjustment or interruption, regardless of study treatment relationship
- Adverse events requiring additional therapy, regardless of study treatment relationship

- Adverse events which are not serious adverse events, regardless of study treatment relationship

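### The SAP's start-date rule for the primary GI count lacks the new-or-worsened condition that Protocol 10.5.3.2 and SAP 2.8.4 carry, so a pre-dose event that only improves could be counted

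*Protocol*

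**What the plan says.** **How events are recorded.** Protocol 8.1.1 collects AEs from consent onward. It splits an event into several records as severity changes. For worsening: "If the event worsens the event should be reported a second time in the CRF noting the start date when the event worsens in toxicity". Moderate and severe events that get better are treated similarly: "if improvement to a lower grade is determined a new entry for this event should be reported in the CRF noting the start date", that date being the day of improvement.

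**How the SAP selects events.** SAP 2.11.1 reports "treatment-emergent AEs starting on or after the date of first study medication", up to 30 days after the last dose. For the primary endpoint, SAP 2.8.1 states: "Selected gastrointestinal disorders will be captured from AE page of eCRFs and PT term will be used". Neither section compares severity with an earlier record or links records of the same event.

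**What the protocol says about the same analysis.** Protocol 10.4, on the primary objective, says "Details regarding the analysis of AEs are described in" Section 10.5.3.2. According to that section, the AE summary tables "will include only AEs that started or worsened during the on-treatment period". It adds: "The incidence of treatment-emergent adverse events (new or worsening from baseline) will be summarized".

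**What the SAP says about the supportive analysis.** SAP 2.8.4, the exposure-adjusted analysis of the same endpoint, limits its numerator to patients whose selected GI events are new or have worsened on treatment. SAP section 4, which lists changes from the protocol's analyses, does not mention dropping that condition for the primary count.

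**The concern.** A start-date rule handles worsening correctly only because Protocol 8.1.1 gives a worsened event a fresh record. It cannot separate that record from an improvement record, which also has a fresh start date. A programmer working from SAP 2.8.1 and 2.11.1 as written would therefore keep both.

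The primary endpoint is a count of children with at least one selected GI event, in a study designed for a minimum of 40. A child whose only qualifying record documents recovery from a pre-dose event would be reported as having a GI event on crushed tablets. The supportive analysis, read as written, would leave the same child out. Two analyses of one endpoint could then have different numerators, with nothing in the plan to say which is intended.

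**Working it through.** **1. The plan's own figures.** Protocol Table 10-1 (repeated as SAP Table 3-1) gives, for n = 40, the Clopper-Pearson interval and the chance of seeing at least one event.

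- P(at least one) = 1 − (1 − p)^40. At p = 3% this is 0.7043, stated as 0.70.
- Interval: B(0.025; x, n − x + 1) to B(0.975; x + 1, n − x), where B is the beta quantile. At x = 10, n = 40 this is 0.127 to 0.412, stated as (0.13, 0.41).

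All ten rows reproduce to two decimals. No stated figure is wrong; the point concerns who is counted.

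**2. One hypothetical child traced through each definition.** Moderate vomiting starts on Day −5, after consent (record A). It becomes mild on Day 3 (record B, start date Day 3). The child has no other GI event.

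| Text | Condition | Record B |
|---|---|---|
| SAP 2.11.1 with 2.8.1 | Starts on or after first dose; listed preferred term | Counted |
| Protocol 10.5.3.2 | Started or worsened on treatment, relative to baseline | Not counted |
| SAP 2.8.4 | New or worsened on treatment | Not counted |

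**3. Effect of a false count.** Each child adds 1/40 = 2.5 percentage points. The true counts below are assumed.

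| True count | Correct | One false count | Two false counts |
|---|---|---|---|
| 4/40 | 10.0% (2.8 to 23.7) | 12.5% (4.2 to 26.8) | 15.0% (5.7 to 29.8) |
| 10/40 | 25.0% (12.7 to 41.2) | 27.5% (14.6 to 43.9) | 30.0% (16.6 to 46.5) |
| 16/40 | 40.0% (24.9 to 56.7) | 42.5% (27.0 to 59.1) | 45.0% (29.3 to 61.5) |

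Adding records can only raise the count, so any error is upward.

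**4. How likely is a false count?** The documents give no rate. Let q be the chance that a child is falsely counted. The expected number is 40q and the chance of at least one is 1 − (1 − q)^40.

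| Assumed q | Expected false counts | P(at least one) |
|---|---|---|
| 0.5% | 0.2 | 0.18 |
| 1% | 0.4 | 0.33 |
| 2% | 0.8 | 0.55 |
| 5% | 2.0 | 0.87 |

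**5. Why q should be small.** All of these must hold:

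- The event carries a selected GI term and is moderate or severe.
- It began or worsened after consent (earlier conditions go to Medical History under Protocol 8.1.1) and before first dose, a screening window of about 14 days.
- It improved on treatment to a lower grade that was still recorded as an event.
- The child had no other qualifying event in 24 weeks plus 30 days, because SAP 2.11.1 counts repeat occurrences of an event once per patient.

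Exclusion criterion 3 (unresolved AEs in previously chelated patients) and criterion 9 (significant GI disease, including uncontrolled vomiting or diarrhea) narrow the group further.

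**The case against.** The strongest reply is that the protocol already settles the matter. Its primary objective section points to 10.5.3.2, which requires a new or worsened event. SAP 2.1 says the data are analysed according to protocol Section 10. SAP 2.8.4 carries the same condition, and SAP section 4 declares no departure from it. The phrase in SAP 2.11.1 sits in a sentence about the severity scale and may only be giving the time window for a term the protocol has defined. Protocol 8.1.1 also treats the improvement record as a further entry for an existing event, so the event itself can be said to have started earlier. Severity and dates are collected, so the protocol rule can be programmed. The SAP also relies on project-standard outputs that are not in the documents.

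Much of this stands. A reader might infer that such events will in fact be counted; the documents do not support that, because the protocol and SAP 2.8.4 point the other way. Nor do they support two further inferences:

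- **Inflated drug-related counts.** Relationship is the investigator's judgement, and nothing suggests that an event with pre-dose onset would be marked as related.
- **Overstated severity.** An improvement record has a lower grade than its parent, so it cannot show an event worse than the child had.

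What the reply does not remove is the gap in the operative text. SAP 2.8.1 and 2.11.1 are the sections that specify the primary count, and the condition is missing there while present in the analysis meant to support it. A programmer could reasonably take that difference as deliberate.

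**Conclusion.** This is a minor but real conflict between definitions. Read literally, the SAP text for the primary count admits an event that began before dosing and only improved. Protocol 10.5.3.2 and SAP 2.8.4 exclude it, and no departure is declared.

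Any error is upward, at 2.5 percentage points per child with n = 40. One child is small against the 28.5-point width of the interval at 10/40 (41.2 − 12.7), and no hypothesis is tested, so no decision rule is affected. The range of 0 to 2 children (0 to 5 points) is an assumption, consistent with an expected count of at most 2.0 if q is 5% or less. Zero is plausible. The case for acting is that the primary numerator should be unambiguous, and making it so is cheap.

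**What to change.** In SAP 2.8.1 and 2.11.1, state that an AE is treatment-emergent only if its original onset is on or after first dose, or if its on-treatment severity exceeds the worst pre-treatment severity of the same event. Link improvement records to the parent event and use the parent's onset date. Apply the same numerator rule in SAP 2.8.4.

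The comparison should be with the worst pre-treatment severity, not with the record just before. Otherwise an event that was severe, then mild before dosing, then moderate on treatment would count although it never exceeded its pre-treatment level.

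Cost: one SAP sentence and the programming to link consecutive records of an event. No new data are needed.
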